APPENDIX 1 DOSE ESCALATION ALGORITHM BASED ON MODIFIED TOXICITY PROBABILITY INTERVAL (MTPI) DESIGN

Tabl	e 1:	a		n	nTPI	Desig	gn ^b D) ecisi	on R	ule w	ith u	p to 1	5 Su	bject	s at a	Dose
					Ν	lumbe	er of si	ubjecs	treate	ed at c	urren	t dose				
		1	2	3	4	5	6	7	8	9	10	11	12	13	14	15
	0	Е	Ε	Ε	Ε	Е	Ε	Е	Ε	Е	Е	Е	Е	Е	Е	Е
	1	D	S	S	S	S	S	E	Ε	Ε	E	E	Ε	E	Е	Е
	2		DU	D	D	S	S	S	S	S	S	S	S	Е	Е	Е
	3			DU	DU	DU	D	S	S	S	S	S	S	S	S	S
LT	4				DU	DU	DU	DU	D	S	S	S	S	S	S	S
Number of subjects with DLT	5					DU	DU	DU	DU	DU	DU	D	S	S	S	S
s wi	6						DU	DU	DU	DU	DU	DU	DU	D	S	S
oject	7							DU	DU	DU	DU	DU	DU	DU	DU	DU
f sul	8								DU	DU	DU	DU	DU	DU	DU	DU
er o	9									DU	DU	DU	DU	DU	DU	DU
amb	10										DU	DU	DU	DU	DU	DU
Ź	11											DU	DU	DU	DU	DU
	12												DU	DU	DU	DU
	13													DU	DU	DU
	14														DU	DU
	15															DU

^a \mathbf{E} = Escalate to next higher dose, S = Stay at the current dose, \mathbf{D} = De-escalate to the next lower dose, U = The current dose is unacceptably toxic

^b Target DLT at MTD = 27% (+/-2%), flexible cohort size

APPENDIX 2 SIMULATION OF MTPI VS 3 + 3 DOSE ESCALATION DESIGNS WITH 6 DOSE LEVELS

Simulations of mTPI and 3+3 designs, shown below, demonstrate that the mTPI design has a greater chance of selecting the correct MTD than the 3+3 design, and treating fewer subjects at sub-optimal doses.

The mTPI uses a set of decision rules guided by simple Bayesian models and requires a clinically relevant pre-determined target DLT rate and an equivalence interval (EI), within which any dose is considered close to the true maximum tolerated dose (MTD). For this study, the selected target toxicity (DLT) rate is 27% and EI [25%, 29%].

The mTPI design makes decisions using the same two observed numbers as the traditional 3+3 design, the number of DLT evaluable subjects and the number of subjects with DLT. Based on these two numbers, unit probability mass is calculated within each of three regions as stated above, and decision is based on which region has the largest unit probability mass:

- E: escalating to the higher dose if interval (0, 25%) has the largest unit probability mass,
- S: staying at the same dose if interval [25, 29%] has the largest unit probability mass,
- D: de-escalating to the lower dose if interval (29, 100%) has the largest unit probability mass.

At the end of the trial, MTD will be picked, by isotonic regression estimation method, to be the dose whose estimated toxicity rate is closest to the target toxicity rate among all the tried doses.

Simulations were performed to examine the operating characteristics of mTPI and 3 + 3 designs for this study. Escalation decisions based on the mTPI are shown in the protocol. Decisions based on the 3+3 design are shown below:

- E: no subject with DLT out of 3 DLT evaluable subjects initially, or at most 1 subject with DLT out of 6 DLT evaluable subjects after adding 3 more subjects.
- S: 1 subject with DLT out of 3 DLT evaluable subjects initially.
- D: at least 2 subjects with DLT out of 3 DLT evaluable subjects initially, or at least 2 subjects with DLT out of 6 DLT evaluable subjects after adding 3 more subjects at this dose

Settings for simulation:

- 6 dose-toxicity scenarios, each of which with a number of 6 (expected) dose levels
- 1000 trials per scenario
- Target toxicity (Pt) for mTPI design: 27% with Equivalence Interval (EI) = [25, 29%]
- mTPI: Cohort sizes of 3-4 at all dose levels, requiring a min of 3 per cohort for escalation decisions. Therefore 4 subjects per cohort and 25% dropout rate were used in simulations.
- Stopping rule for mTPI: When there are already 13 DLT evaluable subjects treated at a dose level, and mTPI suggested decision is to treat more subjects at this dose level, dose escalation can be stopped.

[figure not shown]
Revised Protocol No.: 07 Date: 18-Mar-2019

- Maximum number of DLT evaluable subjects for the study is 30.
- A nominal dose level of -1 is added in the tables to account for the case when de-escalation decision is made from dose level 1. However, the dose level -1 is not used in the simulations.

Dose-Toxicity Curve Scenarios

Six (6) scenarios of dose-toxicity (DLT) curves are selected to cover various possibilities and presented in the following figure with scenario ID shown at the end of line. The target toxicity rate of 0.27 is also superposed in the figure as a horizontal dashed line. The exact numeric values of DLT probability are available in each of the simulation results.

Figure -1: Dose-Toxicity Probability Scenarios

Different Scenarios of Dose-Toxicity Curve

Simulation Results

Simulation results are summarized from all the simulated trials per scenario, and include the following statistics:

- MTD Selected: Frequency of each dose level being selected as MTD.
- Subjects Allocated: Number of subjected being allocated to each dose level.
- DLT rate: The average number of subjects who have DLT across all dose levels.
- Average Sample Size: The average number of subjects across all dose levels.

• Early Stop Prob: mTPI only. The frequency of triggering the mTPI stopping rule during the trial.

Scenario 1				D	ose Lev	/el			DLT	Average	Early
					Rate	Sample	Stop				
										Size	Prob.
		-1	1	2	3	4	5	6			
True DLT		0.05	0.09	0.14	0.18	0.22	0.27				
MTD	3+3	3	7	16	18	19	16	21	15.3		
Selected	mTPI	1	2	12	22	26	22	15	12.3		16
(%)	111111	1	2	12	23	26		15	12.5		10
Subjects	3+3		3.6	4.0	4.0	3.5	2.8	1.7		19.7	
Allocated			2.0			0.0					
(n) mTPI 5.0 5.8 5.5 3.5 1.6 0.4 21.8											
Note: The true MTD is dose level 6, the highest dose level, and all dose levels can be											
considered to be tolerated. In this case, mTPI has a somewhat lower chance of picking the											

highest dose level (15% vs. 21% for 3+3) but greater chance of picking doses closer to the top dose, compared to the 3+3 and lower chance (15% vs. 26% for 3+3) of picking the 2 lowest doses or dose level -1.

Scenario 2		Dose Level							DLT Rate	Average Sample	Early Stop
										Size	Prob.
	-1	1	2	3	4	5	6				
True DLT		0.05	0.10	0.15	0.20	0.27	0.40				
MTD Selected	3+3	3	9	17	23	22	18	9	17.1		
(%)	mTPI	1	2	13	27	27	19	12	13.6		18
Subjects Allocated	3+3		3.6	4.0	4.0	3.5	2.8	1.7		19.1	
(n) $mTPI$ 4.8 6.1 5.7 3.6 1.3 0.3					0.3		21.8				
Note: The true MTD is dose level 5, the second highest dose level, and there is one over-toxic											

dose. In this scenario. mTPI picks the correct MTD about as often as the 3+3, and it picks the 2 lowest doses or dose level -1 less often (29% vs. 16% for the 3+3). The top dose level is selected 3% more frequently by mTPI compared to 3+3.

Scenario 3			D	DLT Rate	Average Sample Size	Early Stop Prob.					
	-1	1	2	3	4	5	6				
True DLT rate			0.05	0.10	0.15	0.27	0.40	0.50			
MTD Selected	3+3	2	9	15	35	27	9	2	18.4		
(%)	mTPI	2	1	11	34	35	14	4	15.2		16
Subjects 3+3 Allocated			3.6	4.0	4.3	3.8	2.0	0.6		18.4	
(n)	[m]P[47 61 62 29 09 0						0		21.7		
Note: The true MTD is dose level 4, and as such, there are three sub-optimal dose levels and											

two over toxic dose levels. mTPI chooses the correct MTD with 35% rate, vs. 27% for 3+3. Selection of over-toxic dose levels is more frequent by mTPI, (18% chance vs. 11% for 3+3), while selection of the 2 lowest doses or dose level -1 is less likely for mTPI (14% vs. 26% for 3+3).

Scenario 4				D	ose Lev	/el			DLT	Average	Early
									Rate	Sample	Stop
										Size	Prob.
		-1	1	2	3	4	5	6			
True DLT	rate		0.10	0.15	0.27	0.40	0.50	0.55			
MTD Selected	3[contact]	9	1	0	23.5		
(%)	mTPI	4	7	31	40	14	4	0	20.3		31
Subjects Allocated	3+3		4.2	4.4	3.7	2.1	0.6	0.1		15.1	
Allocated mTPI 5.9 7.1 5.6 1.6 0.2 0 20.3											
Note: The true MTD is dose level 3. Under this scenario, there are two sub-optimal doses and											
three over-toxic dose levels. mTPI picks the correct MTD 12% more often than 3+3 does, and											
picks doses higher than the MTD 8% more often. Selection of sub-optimal dose levels (lower											

than MTD or level -1) by mTPI is 20% less frequent (42% vs. 62% for 3+3).

Scenario 5		Dose Level							Average Sample Size	Early Stop Prob.	
	-1	1	2	3	4	5	6				
True DLT		0.15	0.27	0.40	0.50	0.55	0.60				
MTD Selected	3[contact]	2	0	0	29.0		
(%)	mTPI	9	26	47	15	3	1	0	26.8		52
Subjects Allocated	3+3		4.9	4.1	2.2	0.6	0.1	0		12.0	
Allocated (n) mTPI 7.9 7.7 2.5 0.					0.3	0	0		18.4		
Note: The true MTD is dose level 2, the second lowest dose level. In this case of one sub-											

Note: The true MTD is dose level 2, the second lowest dose level. In this case of one suboptimal dose level and four over-toxic dose levels mTPI picks the correct MTD almost 20% more often (47% vs. 29% for 3+3). Selection of sub-optimal doses by the mTPI is much less frequent (35% vs. 60% by the 3+3) while over-toxic dose selection is 7% more likely for mTPI than by 3+3.

Scenario 6				D	ose Lev	vel			DLT	Average	2
									Rate	Sample	Stop
		1	4			4	-	6		Size	Prob.
	-1	1	2	3	4	5	6				
True DLT rate			0.27	0.40	0.50	0.55	0.60	0.65			
MTD	3[contact]	1	0	0	0	40		
Selected (%)	mTPI	30	48	19	2	1	0	0	38.7		54
Subjects Allocated	3+3		5.2	2.7	0.7	0.1	0	0		8.7	
(n)	mTPI		9.3	4.0	0.5	0	0	0		13.8	
Note: The true MTD is dose level 1, the lowest dose, which represents an unlikely case when											
only the lowest dose level is considered to be tolerated. mTPI selects the correct MTD more											
often (48% vs. 36% for the 3+3). mTPI picks no dose (dose level -1) at a much lower rate											
(30% vs. 51% for 3+3), but also chooses high dose levels more frequently (22% vs. 12% for											
(50% vs. 51% for 5+5), but also chooses high dose revers more frequently (22% vs. 12% for $3+3)$.											

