Dose escalation decisions will be guided by the cumulative number of subjects who are DLT evaluable and who experience a DLT in the DLT Evaluation Period for all arms (Figure 3.1.1-1 and Appendix 1). If no DLTs are observed in the first dose cohort of Part 1, 3-4 subjects will be enrolled at the next higher dose level. If 1 DLT is observed in 3 or 4 evaluable subjects, this dose level will be expanded by enrolling another cohort of 3-4 at the same dose level. If 2 of 3 or 3 of 4 subjects are observed with DLTs, the next cohort will be enrolled at the next lower dose level. Additional decisions are shown in Figure 3.1.1-1 and Appendix 1. If a decision to treat more subjects at a given dose level is suggested by the mTPI algorithm when there are already at least 13 DLT evaluable subjects treated at the same dose level, a need for further enrollment in the dose escalation phase will be determined by the Sponsor. These same rules will be applied to Schedules B and C. A total of approximately 30 DLT evaluable subjects is expected to be treated per schedule with a total of 90 planned across schedules for the dose escalation phase.

Decisions to escalate, add more subjects to the current dose, de-escalate (with options to re-escalate), or de-escalate and declare the current dose as unacceptable (exceeding the MTD), will be based on the rate of DLTs in evaluable subjects within the 32-35-day DLT evaluation period of Schedule A for Part 1, and within the 35-day DLT evaluation period of Schedules B and C for Part 1 (Appendix 1). At least 3 DLT-evaluated subjects treated at each dose level are required to enable a decision. To account for subjects who may not be able to complete the DLT evaluation period, for reasons other than a DLT, or may not be evaluable for DLT, a fourth subject may be enrolled at this dose level, following agreement between the investigator and Sponsor/Medical Monitor.

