## **5 SAMPLE SIZE AND POWER**

### **5.1 Dose Escalation**

In the dose escalation part of the study, i.e., Part 1, the sample size per dose level and schedule cannot be precisely determined but depends on the observed DLT and the decision rule of mTPI. Between 3 and up to 13 DLT evaluable subjects may be enrolled to a given dose level and schedule. Treating additional subjects beyond the 13 at a dose level in a dose schedule would be unlikely to alter the decision specified by the mTPI algorithm. A total of approximately 30 subjects is expected to be treated per schedule, with a total of 90 planned across schedules for the dose escalation phase. More subjects may be added at a specific schedule if additional dose levels need to be evaluated. Similarly, fewer than 30 subjects may be needed for a different schedule if a smaller number of dose levels are evaluated.

Assuming a 27% acceptable DLT rate, which corresponds to a Beta(1, 2.7) distribution, the risk associated with selecting a dose level as safe given the number of DLTs observed at that dose level based on the posterior probability associated with an observed DLT is dependent on the number of subjects evaluable for DLT at that dose level at the time of the event.

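### Appendix 2's printed mTPI results in Scenarios 1-4 cannot come from its stated cap of 30 DLT-evaluable subjects; they fit about 22 evaluable

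*Protocol*

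**What the plan says.** Appendix 2 compares mTPI with 3+3 over six dose-toxicity scenarios, 1,000 trials each. Section 1.1.6 relies on it for the accuracy of MTD selection.

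- **Cap:** "Maximum number of DLT evaluable subjects for the study is 30".
- **Cohorts:** "Therefore 4 subjects per cohort and 25% dropout rate were used in simulations".
- **Stopping rule:** "When there are already 13 DLT evaluable subjects treated at a dose level, and mTPI suggested decision is to treat more subjects" at that dose, escalation can stop. The early-stop column is the share of trials that trigger this rule.
- **Dose level -1:** a nominal level added to "account for the case when de-escalation decision is made from dose level 1".

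The Scenario 1 allocation row reads "mTPI 5.0 5.8 5.5 3.5 1.6 0.4 21.8". The six dose counts add to the final figure (5.0 + 5.8 + 5.5 + 3.5 + 1.6 + 0.4 = 21.8), so 21.8 is the mean number per trial.

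For the planned size of Part 1, Protocol 3.1.1 says: "A total of approximately 30 DLT evaluable subjects is expected to be treated per schedule with a total of 90 planned across schedules". SAP 5.1 says: "A total of approximately 30 subjects is expected to be treated per schedule, with a total of 90 planned across schedules". Protocol 8.1 agrees with the SAP. The synopsis has both: DLT-evaluable under the escalation rules, plain subjects under sample size.

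**The concern.** Under the listed settings a simulated mTPI trial can end in three ways: the 13-subject rule, de-escalation from dose 1, or the cap. In Scenario 1 the first two account for 16% and 1%, so about 83% of trials must run to the cap. If most trials reach 30 evaluable subjects, a mean of 21.8 is hard to explain.

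The stake is whether the operating characteristics describe the trial that is stated. A reader takes the average size, early-stop and selection rows to be those of a 30-evaluable escalation. The mixed use of evaluable and treated in the text raises a related question: how many evaluable subjects are meant to support each schedule's MTD.

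**Working it through.** **1. The 3+3 rows reproduce.** Simulating 3+3 on the six scenarios gives mean sizes of 19.9, 19.4, 18.3, 15.1, 12.0 and 8.8; Appendix 2 prints 19.7, 19.1, 18.4, 15.1, 12.0 and 8.7. The scenarios are therefore being read correctly.

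**2. Lower bound from the printed figures alone.** Give each kind of ending its smallest possible size:
- early stop: 13, because the rule needs 13 evaluable at one dose;
- dose -1: 3, the minimum for a decision;
- cap: 27, because with cohorts of 4 the code might refuse a cohort that could pass 30 (27 + 4 = 31).

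Mean N ≥ (1 − e − d) × 27 + e × 13 + d × 3, where e is the early-stop share and d the dose -1 share.

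| Scenario | e | d | Calculation | Bound | Printed |
|---|---|---|---|---|---|
| 1 | 0.16 | 0.01 | 22.41 + 2.08 + 0.03 | 24.5 | 21.8 |
| 2 | 0.18 | 0.01 | 21.87 + 2.34 + 0.03 | 24.2 | 21.8 |
| 3 | 0.16 | 0.02 | 22.14 + 2.08 + 0.06 | 24.3 | 21.7 |
| 4 | 0.31 | 0.04 | 17.55 + 4.03 + 0.12 | 21.7 | 20.3 |
| 5 | 0.52 | 0.09 | 10.53 + 6.76 + 0.27 | 17.6 | 18.4 |
| 6 | 0.54 | 0.30 | 4.32 + 7.02 + 0.90 | 12.2 | 13.8 |

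Scenarios 1-4 fall below the bound; Scenarios 5 and 6 are not decided by it. Monte Carlo error does not enter, because both figures come from the same trials. Rounding is small: raising e and d by half a point each lowers the bound by 0.005 × 14 + 0.005 × 24 = 0.19.

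**3. Re-simulation.** Decisions use unit probability mass with a Beta(1,1) prior and exclusion when P(DLT rate > 27%) exceeds 0.95; this agrees with Appendix 1 on the rows compared, 0 to 6 DLTs. Each cohort enrols 4, with a Binomial(4, 0.75) number evaluable. A trial stops at 13 or more evaluable with a decision to stay, and de-escalation from dose 1 ends it. Cells show mean evaluable N, with early-stop % in brackets.

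| Scenario | Printed | 30 evaluable (4,000 trials) | 30 evaluable (20,000 trials) | About 22 evaluable (4,000 trials) | 30 enrolled (20,000 trials) |
|---|---|---|---|---|---|
| 1 | 21.8 (16) | 27.4 (44) | 27.5 (44) | 21.5 (15) | 21.9 (17) |
| 2 | 21.8 (18) | 27.3 (49) | 27.2 (49) | 21.4 (19) | 21.8 (20) |
| 3 | 21.7 (16) | 27.0 (57) | 27.0 (56) | 21.5 (18) | 21.8 (22) |
| 4 | 20.3 (31) | 24.3 (73) | 24.2 (72) | 20.3 (35) | 20.5 (39) |
| 5 | 18.4 (52) | – | 20.5 (82) | – | 18.6 (57) |
| 6 | 13.8 (54) | – | 15.2 (69) | – | 14.3 (56) |

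Varying how dropout is drawn and how de-escalation at dose 1 is handled (1,500 trials per variant) never brought the 30-evaluable mean below 26.7 in Scenarios 1-3. With 30 enrolled, the Scenario 1 allocation is 4.8, 5.7, 5.8, 3.7, 1.5, 0.3 against printed 5.0, 5.8, 5.5, 3.5, 1.6, 0.4.

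**4. Correct-MTD selection at 30 evaluable (20,000 trials).** Scenario 3: 42% (printed 35%). Scenario 4: 44% (40%). Scenario 5: 48% (47%). Scenario 6: 50% (48%).

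**5. The 30 and 90 in the text.** If Appendix 2's 25% dropout applied without replacement, 90 treated would give 90 × 0.75 = 67.5 evaluable, or 22.5 per schedule. Thirty evaluable per schedule would need 30 / 0.75 = 40 treated, 120 in all.

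**The case against.** **Nothing in the conduct of the trial depends on Appendix 2.** Escalation follows the per-dose table in Appendix 1, which does not involve total N. By 21-Dec-2018, 81 subjects had been treated in Part 1 (Section 1.4.4), and this revision already fixes the Part 2 dose and schedule. That stands, and it keeps the point to a documentation correction.

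**The mislabelled cap works against mTPI.** A reader might infer that the case for mTPI over 3+3 is unsafe. It is not. In Scenario 3, mTPI's printed advantage is 35% against 27%, and a true 30-evaluable cap would widen it.

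**The fit to about 22 evaluable is not exact.** With 30 enrolled, simulated early stopping is 5 to 8 points above print in Scenarios 3-5, and dose 6 is selected 8% of the time against 15% printed in Scenario 1, and 4% against 12% in Scenario 2. Some coding choices, such as tie-breaking, are not listed. What was actually run is therefore an inference, and I draw nothing from top-dose selection in Scenarios 1-2. The bound in step 2 does not depend on these choices.

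**The 25% is a simulation setting, not a planned non-evaluable rate.** A reader might infer that Part 1 falls short of its evaluable number or needs 120 subjects. The documents do not support that: counts are approximate, a fourth subject and replacement are allowed, and more subjects may be added. Schedule A had 44 treated by that date, and 44 × 0.75 = 33 would exceed 30. Nor do they show that the wording and the simulation label share one cause.

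**Conclusion.** The stated cap and the printed mTPI results in Scenarios 1-4 cannot both be right. The printed means lie 1.4 to 2.7 subjects below the lowest values that the cap allows, and about 4 to 6 below the simulated values. Early stopping is printed at 16-31% where a 30-evaluable cap gives about 44-73%. This assumes that the three listed endings are the only ones and that the early-stop column means what the appendix says.

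The tables describe a trial of about 22 evaluable subjects. They cannot tell a cap set at about 22 evaluable from one set at about 30 enrolled with 25% dropout.

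The effect on correct-MTD selection is modest: about 6 to 7 points in Scenario 3, in mTPI's favour, and essentially nothing in Scenarios 5-6. The preference for mTPI and the Appendix 1 decision table stand. The second, smaller matter is one of terms: the same 30 and 90 are attached to two different counts, and nothing in the protocol or SAP links them.

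**What to change.** Check the simulation code first, so that no inferred figure goes into the protocol. Then do one of two things:

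- relabel the Appendix 2 cap to what was run, for example 30 enrolled, about 22 evaluable; or
- re-run at 30 evaluable and replace the average-N, early-stop and selection rows, with their notes.

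State the rule for a cohort that would pass the cap and the tie-breaking rule for MTD selection.

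Choose either treated or DLT-evaluable for the 30 per schedule and the 90 in total, and use it in the synopsis, Protocol 3.1.1 and 8.1, and SAP 5.1. If DLT-evaluable is meant, add the number expected to be treated and the non-evaluable rate assumed.

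The cost is a wording change or about an afternoon of simulation. No patients are added and no decision rule changes.

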APPENDIX 3 CYP3A4 GUIDANCE

The lists below are not meant to be all inclusive. Please consult individual drug labels for further information. Additional information is also available at:

http://www.fda.gov/Drugs/DevelopmentApprovalProcess/DevelopmentResources/DrugInteractionsLabeling/ucm080499.htm.

Table 1:	Classification of In	Vivo Inhibitors of CYP E	nzymes
CYP Enzymes	Strong Inhibitors ^a ≥ 5-fold Increase in AUC or > 80% Decrease in CL	Moderate Inhibitors ^b ≥ 2 but < 5-fold Increase in AUC or 50-80% Decrease in CL	Weak Inhibitors ^C ≥ 1.25 but < 2-fold Increase in AUC or 20-50% Decrease in CL
СҮРЗА	Boceprevir, clarithromycin, conivaptan, grapefruit juice, ^d indinavir, itraconazole, ketoconazole, lopinavir/ritonavir, mibefradil, ^e nefazodone, nelfinavir, posaconazole, ritonavir, saquinavir, telaprevir, telithromycin, voriconazole	Amprenavir, aprepitant, atazanavir, ciprofloxacin, darunavir/ritonavir, diltiazem, erythromycin, fluconazole, fosamprenavir, grapefruit juice, ^d imatinib, verapamil	Alprazolam, amiodarone, amlodipine, atorvastatin, bicalutamide, cilostazol, cimetidine, cyclosporine, fluoxetine, fluvoxamine, ginkgo, ^f goldenseal, ^f isoniazid, nilotinib, oral contraceptives, ranitidine, ranolazine, tipranavir/ritonavir, zileuton

Please note that this is not an exhaustive list.

- ^a A strong inhibitor for a specific CYP is defined as an inhibitor that increases the AUC of a substrate for that CYP by equal or more than 5-fold.
- ^b A moderate inhibitor for a specific CYP is defined as an inhibitor that increases the AUC of a sensitive substrate for that CYP by less than 5-fold but equal to or more than 2-fold.
- ^c A weak inhibitor for a specific CYP is defined as an inhibitor that increases the AUC of a sensitive substrate for that CYP by less than 2-fold but equal to or more than 5-fold.
- ^d The effect of grapefruit juice varies widely among brands and is concentration, dose, and preparation dependent. Studies have shown that it can be classified as a "strong CYP3A inhibitor" when a certain preparation was used (eg, high dose, double strength) or as a "moderate CYP3A inhibitor" when another preparation was used (eg, low dose, single strength).
- ^e Withdrawn from the United States market because of safety reasons.

^f Herbal product.

Abbreviations: AUC = area under the concentration-time curve; CYP = cytochrome P450.

	Classification of In								
CYP Enzymes	Strong Inducers ≥ 80% Decrease in AUC	Moderate Inducers 50-80% Decrease in AUC	Weak Inducers 20-50% Decrease in AUC						
СҮРЗА	Avasimibe, ^a carbamazepine, enalutamide, phenytoin, rifampin, St. John's wort ^b	Bosentan, efavirenz, etravirine, modafinil, nafcillin	Amprenavir, aprepitant, armodafinil, echinacea, ^c pioglitazone, prednisone, rufinamide						

Table 2: Classification of In Vivo Inducers of CYP Enzymes

Please note that this is not an exhaustive list.

^a Not a marketed drug.

^b The effect of St. John's wort varies widely and is preparation dependent.

^c Herbal product.

Abbreviations: AUC = area under the concentration-time curve; CYP = cytochrome P450.

Table 3:	Examples of Sensitive In Vivo CYP Substrates and CYP Substrates
	with Narrow Therapeutic Range

CYP Enzymes	Sensitive Substrates ^a	Substrates with Narrow Therapeutic Range ^b
CYP3A(6)	Alfentanil, aprepitant, budesonide, buspirone, conivaptan, darifenacin, darunavir, dasatinib, dronedarone, eletriptan, eplerenone, everolimus, felodipine, indinavir, fluticasone, lopinavir, lovastatin, lurasidone, maraviroc, midazolam, nisoldipine, quetiapine, saquinavir, sildenafil, simvastatin, sirolimus, tolvaptan, tipranavir, triazolam, vardenafil	Alfentanil, astemizole, ^c cisapride, ^c cyclosporine, dihydroergotamine, ergotamine, fentanyl, pimozide, quinidine, sirolimus, tacrolimus, terfenadine ^c

Please note that this is not an exhaustive list.

^a Sensitive CYP substrates refers to drugs whose plasma AUC values have been shown to increase 5-fold or higher when co-administered with a known CYP inhibitor.

^b CYP substrates with narrow therapeutic range refers to drugs whose exposure-response relationship indicates that small increases in their exposure levels by the concomitant use of CYP inhibitors may lead to serious safety concerns (eg, Torsades de Pointes).

^c Withdrawn from the United States market because of safety reasons.

Abbreviations: AUC = area under the concentration-time curve; CYP = cytochrome P450.

